### **5.3 COUNT OUTCOMES**

The count secondary outcomes:

- Number of antibiotic prescriptions (total and split by penicillin and non-penicillin, and antibiotic class),
- Number of hospital admissions (within 56 days of primary event onset), and 12 months

will be analysed using a Poisson mixed effects regression model. The models will include randomised group, age, number of antibiotic prescriptions in the 24 months prior to randomisation (12 months for those recruited to the nested pilot study), and the number of QOF registered diseases as fixed effects. GP practice will be included as a random effect. The adjusted incidence rate ratio between the randomised groups with 95% confidence intervals, and P-values will be obtained from the model.

If there are excess zeros and/or over dispersion in the data, the Poisson model will be run with robust standard errors. If the model fails to converge, a zero-inflated Poisson model and/or a negative binomial model will be considered to analyse these outcomes.

Number of antibiotics split by class is expected to be small in some antibiotic classes in each randomised arm. If it is judged to be too small this will only be presented descriptively.

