#### **2.1.2.3.1 NUMBER OF ANTIBIOTIC PRESCRIPTIONS**

This outcome will be derived from the notes review question “*Please list all the antibiotics the patient was treated with for the above event or symptoms*” (Variable *ABXNAME*), as well as data from the SystmOne report and hospital prescribing report (if available). This outcome will be derived as the number of antibiotic prescriptions up to 12 months post-randomisation. If there is no evidence of antibiotic usage this outcome will be coded as zero. A “prescription” will be considered to be an uninterrupted period of antibiotic use. Where a period of at least 2 days separates prescriptions for the same antibiotic, these will be considered separate prescriptions.

If the patient had a relevant infection event but there is no prescription data for that patient then this outcome will be missing. Patients who also withdrew before 12 months who do not have an antibiotic prescription, and who withdrew consent for notes reviews to be conducted will also have this outcome missing.

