## 2.3 SAMPLE SIZE

The primary outcome was initially treatment response failure defined as the percentage of re-prescription of an alternative antimicrobial within 28 days of an index prescription. A total sample size between 1592 and 2090 participants provided 80-90% power to detect a clinically important absolute difference of 7.9% in re-prescription rate at one year between groups (i.e. reducing from 19.8% in the control group to 11.9% in the PAAP group) at 5% level of significance (2-sided). The sample size had been adjusted assuming 50% of participants will require at least one prescription within 1 year from randomisation and allowing for 10% dropout. Participants are classed as enrolled at the point of randomisation.

The primary outcome was then changed to 'effects of PAAP on penicillin prescribing', defined as 'The proportion of participants who receive prescriptions for a penicillin attending for predefined conditions where a penicillin is the first-line recommended antibiotic (see Appendix II) during the course of routine primary care up to 12 months post randomisation. A total sample of 848 (i.e. 424 per group) was required to provide 90% power to detect an increase in the proportion of penicillin prescription from 4% (Usual Care) to 14% (PAAP) over the year after randomisation at 5% level of significance (2-sided) and 10% attrition. The sample size has been adjusted assuming 50% of participants will require at least one prescription within 1 year from randomisation. At 80% power, the sample size required was 656 (i.e. 328 per group). The table below also provides the sample size required if not all participants have reached 12 months follow-up.

Power	% Difference	Total sample size (all reached 12 months FU)	Total sample size (80% reached 12 months FU)	Total sample size (90% reached 12 months FU)
80%	10%	656	820	729
	15%	372	465	413
90%	10%	848	1060	942
	15%	472	590	524

Results from our recent analysis, using data extracted from the SystmOne database, suggested that there were an average of 110 patients per average practice size of 6000 who fulfilled our inclusion criteria.

- 1) Adults (over 18 years),
- 2) Penicillin allergy in electronic health records,
- 3) And in receipt of a penicillin, cephalosporin, tetracycline, quinolone, or macrolide class antimicrobial in the previous 24 months.

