## **6.3 EXCLUDED PARTICIPANTS WHO DID NOT HAVE COMPLETE FOLLOW-UP**

Participants recruited towards the end of the recruitment period may not have been followed-up for the full 12 months of the planned follow-up period. If there are any participants who were not followed-up for 12 months, the primary analysis (section 4.1) will be re-run with these participants excluded from the analysis.

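### The count models in SAP section 5.3 report an incidence rate ratio without any term for observed time, although the SAP anticipates follow-up shorter than 12 months

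*SAP*

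**What the plan says.** Section 5.3 covers two sets of counts: antibiotic prescriptions (total, penicillin and non-penicillin, and by class), and hospital admissions (within 56 days of a primary event, and over 12 months). They "will be analysed using a Poisson mixed effects regression model". On the terms: "The models will include randomised group, age, number of antibiotic prescriptions in the 24 months prior to randomisation"; the number of QOF diseases and a random effect for GP practice complete the list. On the effect measure: "The adjusted incidence rate ratio between the randomised groups with 95% confidence intervals, and P-values will be obtained from the model". For over-dispersion: "If there are excess zeros and/or over dispersion in the data, the Poisson model will be run with robust standard errors". Zero-inflated Poisson and negative binomial models are the fallback if fitting fails. No exposure term is named for any of these.

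On follow-up, section 6.3 states: "Participants recruited towards the end of the recruitment period may not have been followed-up for the full 12 months of the planned follow-up period". Section 2.3 adds: "The table below also provides the sample size required if not all participants have reached 12 months follow-up", with columns for 80% and 90% reaching 12 months.

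On derivation, section 2.1.2.3.1 states: "This outcome will be derived as the number of antibiotic prescriptions up to 12 months post-randomisation". A participant with no evidence of use is coded zero, with no condition on time observed. One group is set to missing instead: those who withdrew before 12 months, have no prescription and also withdrew consent to notes review. Section 2.1.2.4 codes admissions as zero where there is no evidence of one and gives no missing-data rule.

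The opening of section 6 confines sensitivity analyses to the primary outcome, so the exclusion of incomplete follow-up in section 6.3 does not reach the counts.

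**The concern.** A Poisson model with a log link and no offset models the expected count per participant. Its exponentiated arm coefficient is a ratio of mean counts, and becomes a ratio of rates only when mean time at risk is equal between arms. The SAP names a rate ratio, foresees participants with partial time, and neither enters that time in the model nor checks its effect on these outcomes.

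The trial is open label, so death and withdrawal of notes-review consent after allocation could differ by arm. If partial time is kept in the model, the arm observed for less time would appear to use fewer antibiotics or have fewer admissions. The missing-data rule for prescriptions is a second problem: two participants who withdraw notes-review consent on the same day are treated differently according to whether a prescription had already been recorded. The one with a prescription stays in with a positive count; the one without is dropped. Selection then depends on the outcome itself.

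**Working it through.** The SAP gives no numerical figure for the count outcomes, so there is none to reproduce. Its follow-up columns in section 2.3 are simple inflations of the overall total: 848/0.8 = 1060 and 848/0.9 = 942. They are planning scenarios for the whole trial and are not split by arm.

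**Step 1. What the model estimates.** Let the event rate be constant, s the proportion with full follow-up in an arm, and f the fraction of a year observed in the others. Mean observed time is m = s + (1 − s)f. Without an offset, estimated ratio = true rate ratio × m(PAAP) / m(usual care).

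**Step 2. Numbers at a true ratio of 1.00.** The 80%, 90% and 100% figures are taken from section 2.3. Their assignment to arms, and f, are assumptions.

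| Complete, usual care v PAAP | f = 0.25 (3 months) | f = 0.50 (6 months) | f = 0.75 (9 months) |
|---|---|---|---|
| 80% v 80% | 0.85/0.85 = 1.00 | 0.90/0.90 = 1.00 | 0.95/0.95 = 1.00 |
| 90% v 80% | 0.85/0.925 = 0.919 | 0.90/0.95 = 0.947 | 0.95/0.975 = 0.974 |
| 80% v 90% | 0.925/0.85 = 1.088 | 0.95/0.90 = 1.056 | 0.975/0.95 = 1.026 |
| 100% v 80% | 0.85 | 0.90 | 0.95 |

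**Step 3. Simulation check.** Settings: 424 per arm (section 2.3), 2000 runs, robust standard errors, no covariates or practice effect; assumed rate of 1 per year, gamma frailty with variance 1, f = 0.5, true ratio 1.00.

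| Complete, usual care v PAAP | No offset: ratio (rejection rate) | Offset: ratio (rejection rate) |
|---|---|---|
| 80% v 80% | 1.00 (4.7%) | 1.00 (4.8%) |
| 90% v 80% | 0.947 (9.3%) | 1.00 (5.5%) |
| 100% v 80% | 0.90 (19.7%) | 1.00 (4.3%) |

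The robust standard errors planned in section 5.3 were used here. They leave the point estimate where it was.

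**Step 4. The missing-data rule in section 2.1.2.3.1.** As an extreme case, suppose everyone with short follow-up had withdrawn notes-review consent, so that those with a zero count are dropped. Under the Step 3 assumptions a participant observed for half a year has a zero count with probability 1/(1 + 0.5) = 2/3, so one third of the short-follow-up group is kept. All events are kept. Per participant randomised:
- Mean count among those kept: 80% complete, 0.90/(0.80 + 0.20/3) = 1.038; 90% complete, 0.95/(0.90 + 0.10/3) = 1.018; 100% complete, 1.00.
- Without an offset: 90% v 80% gives 1.038/1.018 = 1.02, and 100% v 80% gives 1.04 (simulated: 1.018 and 1.040).
- With an offset, the denominators are the time kept: 0.90/(0.80 + 0.20/6) = 1.080; 0.95/(0.90 + 0.10/6) = 1.036. The ratios are 1.080/1.036 = 1.04 and 1.08 (simulated: 1.040 and 1.082).

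The error changes sign, and an offset on its own makes it larger, because only event-free short follow-up has been removed.

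**Step 5. A limit of the offset.** If the effect is delayed (assumed: none for 3 months, rate ratio 0.7 afterwards) the 12-month ratio is 0.25 + 0.75 × 0.7 = 0.775. With 80% complete in both arms and f = 0.5, both models give (0.8 × 0.775 + 0.2 × 0.425)/0.90 = 0.783, where 0.425 = 0.25 + 0.25 × 0.7. An offset does not correct this small shift, which is one reason for also running a complete-follow-up analysis.

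**The case against.** The case for leaving the plan alone has real force.

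- **Balance.** The only cause of short follow-up that section 6.3 names is late recruitment. Recruitment date precedes allocation, and 1:1 minimised allocation (section 2.4) should balance it. The 80% v 80% rows show no bias then, given a constant rate. This stands.
- **Record-based outcomes.** Prescriptions come from SystmOne, notes review and hospital reports, and people who miss the clinic are still followed. Stopping calls need not shorten observation; withdrawing notes-review consent can. Patients with an estimated life expectancy under one year are excluded, which limits deaths. This narrows the exposure to bias without removing it.
- **Terminology.** Incidence rate ratio is the customary label for an exponentiated Poisson coefficient, and a ratio of mean counts over 12 months is a legitimate target. But the plan does not say that this is its target, nor how partial time enters it.

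Two stronger readings are tempting and are not supported. A reader might infer that short follow-up is generally counted as a full event-free year. It is not: observed events still count, and event-free participants who withdrew notes-review consent are missing, not zero, for the prescription counts (section 2.1.2.3.1) and for the primary outcome (section 2.1.1). A reader might also infer that the ratios will be biased, in favour of the arm followed for less time. Nothing in the SAP shows that follow-up differs by arm, and Step 4 shows that the direction can reverse.

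The version history mentions an adjustment for time in study at version 0.4. That is superseded text and is not counted as a contradiction.

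**Conclusion.** The point holds in a limited form. Section 5.3 names a rate ratio but specifies models that estimate a ratio of mean counts, and no planned analysis shows whether the difference matters for these outcomes. The two coincide if mean observed time is equal between arms. They diverge by the ratio of mean observed times if death or withdrawal of notes-review consent differs by arm and the partial time is kept in the model. With 90% v 80% complete, that is an error of about 3% to 8% for short follow-up of 9 down to 3 months. The outcome-dependent missing rule works in the opposite direction. These sizes rest on assumed splits by arm, assumed lengths of follow-up and a constant rate; the actual size and direction cannot be known from the SAP.

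The affected outcomes are secondary or exploratory. The change is still worth making: it is standard, costs little, and leaves the ratio essentially unchanged if follow-up proves balanced. The primary outcome is not part of this conclusion. Section 6.3 already gives it a check. A complementary log-log model with an offset would be an optional extra; it assumes a constant hazard and does not estimate the relative risk in section 4.1.

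**What to change.** 1. Define the end of observation for each participant as the earliest of 12 months, death, withdrawal of notes-review consent, and data cut-off.
2. Add the natural log of observed time from randomisation as an offset in the section 5.3 models for number of prescriptions and for all 12-month admissions, including the fallback models.
3. Keep participants who withdraw notes-review consent with the count and time observed up to that date, zero counts included, whether or not they had an event. Steps 2 and 3 belong together, because the offset alone can enlarge the error. Section 2.1.2.3.1 already retains such participants when they have a prescription.
4. For admissions within 56 days of a primary event, time since randomisation is not the period at risk. Base exposure on the observed post-event window, or label the result a ratio of mean counts.
5. Extend the complete-follow-up analysis in section 6.3 to the count outcomes, and report observed time by arm.

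The cost is one derived end date and time variable, a post-event window if that option is chosen in item 4, a revised missing-data rule, and a repeat of the count models. The dates needed are of a kind the trial should already hold; no new data collection is expected.

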## **6 SENSITIVITY ANALYSIS**

Sensitivity analyses will be conducted with respect to the primary outcome only (unless explicitly stated, see 6.6) and will explore the sensitivity of results departure from the randomisation policy, missing data, and the effect of the COVID-19 pandemic.

### **6.1 AS TREATED (AT)**

Participants were analysed in their randomly assigned intervention arm for the primary analysis regardless of whether they received the intervention or not. A sensitivity analysis will be conducted analysing participants depending on whether they received the allocated intervention or not. The definition of the “as treated” (AT) analysis population is described in section 3.3.

The model used in the primary analysis (section 4.1) will be re-run on the AT group, with age, number of antibiotic prescriptions in the 24 months (12 months for those recruited to the nested pilot study) prior to randomisation, and the number of QOF registered diseases as fixed effects. GP practice will be included as a random effect. The adjusted relative risk between the AT groups and the corresponding 95% confidence intervals will be obtained from the model and reported alongside the associated P-value.

## **6.2 FACTORS THAT PREDICT MISSINGNESS**

A logistic regression analysis, described in section 4.2 will be conducted to investigate factors (if any) that are predictive of non-response of the primary outcome. If any factors are associated with non-response, the model used in the primary analysis (section 4.1) will be re-run with these factors included in the model as fixed effects, alongside randomised group, age, number of antibiotic prescriptions in the 24 months prior to randomisation (12 months for those recruited to the nested pilot study), and the number of QOF registered diseases as fixed effects, and GP practice as a random effect. The adjusted relative risk between the randomised groups and the corresponding 95% confidence intervals will be obtained from the model and reported alongside the associated P-value.

## **6.3 EXCLUDED PARTICIPANTS WHO DID NOT HAVE COMPLETE FOLLOW-UP**

Participants recruited towards the end of the recruitment period may not have been followed-up for the full 12 months of the planned follow-up period. If there are any participants who were not followed-up for 12 months, the primary analysis (section 4.1) will be re-run with these participants excluded from the analysis.

## **6.4 EXCLUDING PARTICIPANTS WHO HAD DELAYED PAAP**

There may be cases where a participant who was randomised to PAAP did not receive PAAP for quite some time. The primary analysis (section 4.1) will be re-run with the participants who were delayed in receiving the PAAP by more than 3 months (90 days) excluded from the analysis population.

# **7 SUBGROUP ANALYSES**

No subgroup analysis was planned for in the protocol; however, the trial team suggested 3 subgroups of interest:

- i) Age (<65 years versus  $\geq 65$  years),
- ii) Number of QOFs at baseline (<2 versus  $\geq 2$ ),
- iii) And IMD (split at the median).

The primary analysis (see section 4.1) will be rerun with an additional two-way interaction between randomised group and subgroup as a fixed effect. The adjusted relative risk between the randomised groups in each level of the subgroup and the corresponding 95% confidence intervals will be obtained from the model which will be reported alongside the associated P-value for the interaction. The results of the subgroup analyses will be presented in a forest plot.

# **8 EXPLORATORY ANALYSIS**

The analysis for the hospital outcomes described above (hospital admissions, number of hospital admissions, and length of hospital stay) in the 56 days following a primary event will be re-conducted for all hospital admissions during the 12 months trial period. This analysis should be considered exploratory.

## **9 SAFETY ANALYSIS**

All participants randomised will be included in the safety analysis. The safety analysis will be conducted on an as treated (AT) basis, participants will be analysed by the intervention they actually received instead of the intervention they were randomised to receive. The safety analysis will be conducted on the AEs and SAEs as appropriate.

Safety of the trial participants is paramount. Consequently, PAAP testing is performed in a hospital clinic to mitigate any risk of dealing safety and swiftly with anaphylaxis or other serious reaction to the oral challenge test, this is standard care in hospital clinics where suitably qualified and trained personal and equipment are at hand. Access details to the on-call immunology staff are given to all participants as is this standard of care for all penicillin-allergy assessments to ensure appropriate management of problems that might develop after the participants return home.

Telephone calls by the research team at the following time-points collected information on adverse events (AEs) associated with the penicillin allergy test (skin test and/or oral challenge test): 4-6 days, and 28-30 days after penicillin allergy testing.

Adverse events occurring up to 28 days after an antibiotic prescription from their general practitioner for any pre-defined infections listed in the protocol is captured through the participant diary and telephone calls by the research team after the start of an antibiotic prescription.

The frequency of adverse events (AEs) and adverse reactions (ARs) will be summarised. A list of all adverse events and reactions experienced during the trial will be presented including information on the type of event, AE description, start date of AE, end date of AE, severity of the event, outcome of the AE, event related to treatment, what the adverse reaction was too, description of AR, what test the participant had (skin/OCT/both), and whether or not the participant went on to be de-labelled as being allergic to penicillin. Participants that went on to be de-labelled will be highlighted in the table of adverse events.

In addition to summarising all adverse events and reactions, only those that occurred during 3 days post antibiotic follow-up will be presented.

If the list and description of the adverse events could potentially unblind the report, this will not be presented in the blinded version of the report, only the summary statistics will be provided. In this case the detailed list of adverse events will only be presented in the unblinded report, which will only be prepared when the blinded report has been signed off.

A serious adverse event (SAE) is any untoward medical occurrence that:

- Results in death,
- Is life-threatening,
- Requires inpatient hospitalisation or prolongation of existing hospitalisation,
- Results in persistent or significant disability/incapacity,
- Or consists of a congenital anomaly or birth defect.

Other important medical events' may also be considered serious if they jeopardise the participant or require an intervention to prevent one of the above consequences.

- Anaphylaxis to an antibiotic will be considered an SAE as part of the ALABAMA trial.

NOTE: The term "life-threatening" in the definition of "serious" refers to an event in which the participant was at risk of death at the time of the event; it does not refer to an event which hypothetically might have caused death if it were more severe.

The number and percentage of participants experiencing at least one SAE will be reported by the intervention they received (rather than the intervention they were randomised to receive) and will be analysed using a Fisher's Exact test if possible. The total number of SAEs per AT group will be reported for each serious adverse event. The total number of SAEs per AT group will also be reported.

Any SAEs identified during the ALABAMA trial need to be assessed for their relatedness to:

1. Penicillin Allergy Assessment (PAA)
2. An antibiotic prescription\* for any of the pre-defined infections listed in Appendix G of the protocol and Appendix II of this document.

\*Because patients may have more than one antibiotic prescription during the ALABAMA trial, the relatedness of SAEs was assessed in relation to their most recent antibiotic prescription for any pre-defined infections.

SAE description, start date of SAE, stop date of SAE, severity of the event, reason the event was classified as serious, event related to intervention, was the event unexpected, outcome of the SAE, allocated intervention group, and received intervention, will be reported for each serious adverse event.

If the list and description of the serious adverse events could potentially unblind the report this will not be presented in the blinded version of the report. In this case the detailed list of serious adverse events will only be presented in the unblinded report, which will only be prepared when the blinded report has been signed off.

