### **3.3 DEFINITION OF POPULATION FOR ANALYSIS**

The primary analysis population will include all randomised patients in the treatment arm they were assigned to, regardless of treatment received. All data will be included in the analysis as far as possible, though there will inevitably be the problem of missing data due to withdrawal, loss to follow-up, or non-response to questionnaire items.

Participants withdrawn for post-randomisation ineligibility will be excluded from the analyses. Those randomised but who were not eligible at the PAAP clinic will not be included in the analysis population. Those who were eligible but decided not to go ahead with PAAP will be included in the analysis population.

The primary analysis will also be carried out on the “as treated” (AT) analysis population. All participants who were allocated to PAAP and had exposure to the test (i.e., they completed either the skin test or oral challenge test, or both), will be included in the as-treated PAAP arm. Those participants who were randomised to PAAP but did not have a test or who were randomised to usual care will be included in the usual care arm.

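### The only between-group SAE comparison counts PAAP-allocated participants who were never tested as usual care, and no SAE comparison by randomised arm is planned

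*SAP*

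**What the plan says.** Three statements in the SAP fix the safety comparison.

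- **Population.** Section 9: "All participants randomised will be included in the safety analysis. The safety analysis will be conducted on an as treated (AT) basis".
- **Grouping.** Section 9 adds that "participants will be analysed by the intervention they actually received instead of the intervention they were randomised to receive". Section 3.3 defines the groups. A participant allocated to PAAP counts as PAAP if "they completed either the skin test or oral challenge test, or both". Those "randomised to PAAP but did not have a test or who were randomised to usual care will be included in the usual care arm".
- **Test.** Section 9 states that the number and percentage of participants with at least one SAE "will be reported by the intervention they received (rather than the intervention they were randomised to receive"), with a Fisher's exact test if possible. SAE totals are also by as-treated group.

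The SAE listing in section 9 shows allocated and received intervention for each event, but no SAE comparison by allocated arm is planned.

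Section 3.3 also has a rule that does not fit with section 9: "Those randomised but who were not eligible at the PAAP clinic will not be included in the analysis population". It further excludes participants withdrawn for post-randomisation ineligibility.

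**The concern.** Testing happens after randomisation, and section 6.4 accepts that the delay can be long. Whether a PAAP-allocated participant is tested can therefore depend on what happens in between. Someone who dies, or becomes too ill to attend, is never tested, and under the as-treated rule that SAE is counted under usual care. Any SAE during the rest of follow-up in an untested PAAP participant moves the same way. A participant who has an SAE and is tested later stays in the PAAP group. Nobody allocated to usual care can enter the as-treated PAAP group, because section 3.3 restricts it to those allocated to PAAP.

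The transfer is thus one-way and can be triggered by the outcome being compared. Fisher's exact test makes no adjustment for it. At stake is the formal between-group statement on SAEs, for a pathway where section 9 itself gives participant safety the highest priority.

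**Working it through.** **Plan's own figure.** The point disputes no figure in the SAP. The 424 per group in section 2.3 is used only as a denominator in step 4. It reproduces: a continuity-corrected comparison of 4% with 14% at 90% power needs 190 per arm, and 190/(0.5 × 0.9) = 422.2, so 423 per arm or 846 in total, against 848 stated.

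**Step 1: where each participant goes.**

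| Participant | Section 3.3, main analysis population | Section 9, SAE comparison |
|---|---|---|
| PAAP, tested | PAAP | PAAP |
| PAAP, eligible, not tested | PAAP | Usual care |
| PAAP, found ineligible at clinic | Excluded | Usual care if all randomised are included; excluded if section 3.3 governs |
| Usual care | Usual care | Usual care |

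In the third row the two sections conflict. Under neither reading is the SAE of a participant found ineligible at the clinic counted in the PAAP arm.

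**Step 2: formula.** Let u be the share of the PAAP arm not tested, s_t the SAE risk in those who would be tested, and s_u the risk in those who would not. With no true effect, both randomised arms have risk r = (1 − u)s_t + u·s_u, so the as-randomised risk ratio is 1.00. Under the as-treated rule:

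- PAAP = s_t
- usual care = (r + u·s_u)/(1 + u)
- usual care minus PAAP = 2u(s_u − s_t)/(1 + u)

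The sign of the bias is the sign of s_u − s_t. It is zero if the risks are equal and reverses if the untested are at lower risk.

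**Step 3: results.** The SAP gives neither an SAE rate nor an untested share, so every input here is an assumption: s_t = 8%, s_u = 8%, 16% or 24%, and u = 5%, 10% or 20%.

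| u | s_u | r, both arms | As-treated PAAP | As-treated usual care | Risk ratio |
|---|---|---|---|---|---|
| any | 8% | 8.0% | 8.0% | 8.0% | 1.00 |
| 5% | 16% | 8.4% | 8.0% | 9.2/1.05 = 8.8% | 0.91 |
| 5% | 24% | 8.8% | 8.0% | 10.0/1.05 = 9.5% | 0.84 |
| 10% | 16% | 8.8% | 8.0% | 10.4/1.10 = 9.5% | 0.85 |
| 10% | 24% | 9.6% | 8.0% | 12.0/1.10 = 10.9% | 0.73 |
| 20% | 16% | 9.6% | 8.0% | 12.8/1.20 = 10.7% | 0.75 |
| 20% | 24% | 11.2% | 8.0% | 16.0/1.20 = 13.3% | 0.60 |

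**Step 4: an excess in the PAAP arm.** Take 424 per arm, 42 PAAP participants untested with 30% SAE risk (13 with an SAE), and 10% risk in everyone else, including all of usual care. This assumes a real excess among the untested.

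- As randomised: (38 + 13)/424 = 51/424 against 42/424, risk ratio 1.21, Fisher P = 0.38.
- As treated: 38/382 against (42 + 13)/(424 + 42) = 55/466, risk ratio 0.84, P = 0.44.

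Neither result is significant, but the direction reverses because 13 participants with SAEs move to the comparator.

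**The case against.** **Serious harm is partly compared as randomised.** A reader might infer that nothing in the SAP compares serious harm by allocated arm. That is not so. Section 1.4.2 labels hospital admissions and mortality as safety outcomes, sections 5.1 to 5.3 model them by randomised group, and death and inpatient hospitalisation are two of the SAE criteria in section 9. This stands and lowers the severity. It does not fill the gap completely. Those models use the section 3.3 population, which drops participants found ineligible at the clinic, and only PAAP participants have a clinic visit. The admission outcomes in section 2.1.2.4 cover the 56 days after a primary event, and the analysis of all admissions is exploratory (section 8).

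**The direction is not certain.** A reader might infer that PAAP must look safer. The SAP does not support that. The untested include people who declined or did not attend, and nothing shows that they are at higher risk. Tested participants also get extra calls at 4-6 and 28-30 days after testing, which could raise detected events in the as-treated PAAP group. The net direction cannot be established from the document.

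**Participants found ineligible at the clinic are not plainly moved to usual care.** Section 3.3 read alone would exclude them. What stands is the conflict.

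**As-treated safety reporting is a common convention.** It suits reactions to the test, and an event before testing cannot be such a reaction. The listing also lets a reader trace each misplaced SAE. Both points stand, and they are reasons to keep the as-treated table. But a listing is not a comparison. Nor is every pre-test event necessarily unrelated to the pathway, since section 2.2.2 shows that preparation can involve withholding other medicines.

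**Conclusion.** The point holds as a should-fix. On the SAP's wording, SAEs in PAAP-allocated participants who are never tested are counted under usual care in the only between-group SAE comparison, and no transfer in the other direction is possible. The bias favours PAAP if untested participants have a higher SAE risk. That is plausible, because illness can be the reason for not being tested, but the SAP does not quantify it. Under the assumed risks the as-treated risk ratio runs from 0.91 to 0.60 with no true effect, and it is 1.00 if the risks are equal. The inconsistency between sections 3.3 and 9 over participants found ineligible at the clinic needs no assumption. The primary efficacy analysis is not affected by the safety grouping.

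**What to change.** 1. In section 9, add as the main between-group SAE comparison the number of participants with at least one SAE by randomised arm (Fisher's exact test). Include everyone randomised, with those found ineligible at the clinic kept in their assigned arm.
2. Keep the as-treated table as a description of test safety, with untested PAAP participants shown separately rather than merged with usual care.
3. Reconcile sections 3.3 and 9 on who is in the safety population, stating whether the section 3.3 exclusions apply to efficacy only.

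The cost is SAP wording and one extra table. No new data are needed, because allocated and received intervention are already to be reported for each SAE. The added comparison removes the selection by test status. It does not remove any difference in event detection caused by the extra post-test calls, which should be noted when the results are read.
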